9.2. Setting

IQVIA PharMetrics[®] Plus is a longitudinal health plan database of adjudicated medical and pharmacy claims, including patient enrollment data for national and sub-national health plans and self-insured employer groups in the US. Administrative claims and enrollment data available during 01 January 2016 and 31 December 2022 will be used in this study.

9.2.1. Inclusion Criteria

Patient records must meet all of the following inclusion criteria to be eligible for inclusion in the study:

- 1. Individuals of approximately 15-30 years old (using July 1 of birth year) enrolled in a health plan available in PharMetrics Plus database during 01 January 2016 and 31 December 2021.
- Individuals having at least 1 dose of MenACWY during 01 January 2016 and 31 December 2021.

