9. RESEARCH METHODS

9.1. Study Design

This is a retrospective cohort study using health care administrative claims data as described in Section 9.4 Data Sources.

Adolescents and young adults approximately 15 to 30 years of age at their individual time zero (calculated based on birth year) will be identified from administrative claims during 01 January 2016 and 31 December 2021.

The exposure cohort will be the individuals who have received at least 1 dose of Trumenba and at least 1 dose of MenACWY (Menactra[®], Menveo[®], or MenQuadfi[®]) prior to the Trumenba vaccination, between 01 January 2016 and 31 December 2021. The index date (zero time) for the exposed cohort is the last date of vaccination, and the cohort will be followed from 14 days after vaccination to the end of the study period (31 December 2022). The individuals in the cohort will be censored by the event of interest, death date (if known), plan disenrollment (if known) or the end of the study period, whichever comes first.

PFIZER CONFIDENTIAL CT24-WI-GL02-RF02 4.0 Non-Interventional Study Protocol Template For Secondary Data Collection Study 01-Jun-2022 Page 11 of 22

The reference cohort will be those with at least 1 dose of MenACWY vaccine, but no doses of Trumemba during the observation period, received between 01January 2016 and 31 December 2021. The MenACWY-only vaccinated cohort is used as a reference cohort rather than an unvaccinated cohort in order to help control for theoretical differences in health seeking and risk behaviors between vaccinated and unvaccinated individuals. The index date (zero time) of the reference cohort is the last dose of MenACWY and these individuals will be followed from 14 days after zero time until the earliest occurrence of the following: outcome of interest, death date (if known), plan disenrollment (if known) or 31 December 2022 (end of study period).

The outcomes of interest are gonococcal and chlamydial infections and only the first episode within the study period will be considered as event in case of repeated infections.

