9.2.2. Exclusion Criteria

Patients meeting any of the following criteria will not be included in the study:

Individuals having any dose of Bexsero at any time during 01 January 2016 and 31 December 2021 and prior to the study

Individuals with missing demographic variables or dates of outcome diagnoses or vaccine administration (listed in Section 9.3).

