9.8. Quality Control

Only observed data will be used in measuring study variables. It is anticipated that demographic information will be available for nearly all individuals in the study population. All other variables will be defined based on the presence of specific data (eg, diagnosis, procedure, and drug codes) in the analytic file; the absence of such data will be assumed to indicate the absence of the characteristic/event captured by the variable.

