9.9. Strengths and Limitations of the Research Methods

Strengths

A significant strength of observational retrospective analyses is that they provide a better understanding of the study population in real world clinical practice as compared to the controlled conditions of a clinical trial.

Limitations

There are several limitations in this study. Given that this is an observational study using health care administrative claims data, residual confounding due to missing or unmeasured information is possible. To examine this, we will assess the effect of meningococcal vaccination on another sexually transmitted disease occuring, at the same age group, as reference disease outcome. If the HRs in any of these models are less than 1.0, it would indicate that residual confounding exists and may result in adjustment of our vaccine effectiveness (VE) estimates.

Second, health care administrative claims data will be available from 01 January 2016 through 31 December 2022. It is possible that some participants may have received a Trumenba vaccination prior to January 1, 2016 or during a period in which we do not have their claims data and be misclassified as unvaccinated with Trumenba. This may underestimate Trumenba vaccine effectiveness because the Men-ACWY-only cohort will include Trumenba vaccinated patients.

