4.1 FULL ANALYSIS SET

The full analysis data set will consists of all subjects who met all inclusion/exclusion criteria. Any participant who will not meet the inclusion/exclusion criteria will be excluded from the full analysis set.

Inclusion criteria

 Individuals of approximately 15-30 years old (using July 1 of birth year) enrolled in a health plan available in PharMetrics Plus database during 01 January 2016 and 31 December 2021

PFIZER CONFIDENTIAL CT24-WI-GL03-RF03 2.0 Non-Interventional Statistical Analysis Plan For Secondary Data Collection Study 01-Jun-2020 Page 7 of 28 Individuals having at least one dose of MenACWY during 01 January 2016 and 31 December 2021. MenACWY vaccination will be identified using CPT codes and NDCs listed in Appendix Table 3.

Exclusion criteria

Patients meeting any of the following criteria will not be included in the study:

- Individuals having a dose of Trumemba before their first dose of MenACWY during 01 January 2016 and 31 December 2021
- Individuals having any dose of Bexsero at any time during 01 January 2016 and 31 December 2021. Bexsero vaccination will be identified using CPT codes and NDCs listed in Appendix Table 5.
- 3. Individuals with missing demographic variables or dates of outcome diagnoses or vaccine administration.

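### No enrolment before zero time is required, so missed Trumenba doses dilute the reference cohort, missed Bexsero may lower VE further, and the plan measures neither

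*Protocol*

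**What the plan says.** Protocol 9.2.1 accepts a person "enrolled in a health plan available in PharMetrics Plus database during 01 January 2016 and 31 December 2021" with at least one MenACWY dose in the same window. SAP 4.1 repeats this: "Individuals having at least one dose of MenACWY during 01 January 2016 and 31 December 2021". Neither sets a length of enrolment or a look-back before zero time.

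The cohorts differ in what must be observed (Protocol 9.1). Exposed people need a MenACWY dose "prior to the Trumenba vaccination, between 01 January 2016 and 31 December 2021", so two claims in sequence. Reference people need one MenACWY claim "but no doses of Trumemba during the observation period".

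For variables defined by codes, Protocol 9.8 states that "the absence of such data will be assumed to indicate the absence of the characteristic/event captured by the variable".

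The Bexsero exclusion differs between the documents. Protocol 9.2.2 removes "Individuals having any dose of Bexsero at any time during 01 January 2016 and 31 December 2021 and prior to the study". SAP 4.1 removes "Individuals having any dose of Bexsero at any time during 01 January 2016 and 31 December 2021" and has no reference to earlier doses. Protocol 9.2 limits the data to 01 January 2016 onward, and neither document says how earlier doses would be found.

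Protocol 9.9 concedes that a person may have had Trumenba before 2016 or "during a period in which we do not have their claims data and be misclassified as unvaccinated with Trumenba", and that this may underestimate VE. It does not mention missed Bexsero. The only sensitivity analysis of the primary endpoint (SAP 7.2.1.2) concerns gonorrhoea and chlamydia coinfection.

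**The concern.** A reference person can join a plan, receive MenACWY soon afterwards and enter follow-up with almost no claims history. Any earlier Trumenba or Bexsero is then invisible and counted as absent. An exposed person has at least the time between the two claims under observation.

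For Trumenba in the one-dose analysis the direction is fixed. An exposed person with a further unseen dose is still exposed, so a missed dose can change a person's group only by placing a vaccinated person in the reference cohort. That lowers the reference rate if the vaccine works, and moves VE toward zero.

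For Bexsero the effect depends on how the missed doses divide between the cohorts. Protocol 7 cites effectiveness against gonorrhoea of 40% (full dose) and 26% (one dose). If missed Bexsero is commoner in the reference cohort, VE falls, and nothing stops it at zero. This matters because the study follows up a cited fHbp effectiveness of only 3%.

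The chlamydia comparison would not be expected to show the problem. If these vaccines have no effect on chlamydia, misclassified vaccination leaves that hazard ratio unchanged. The rule in Protocol 9.9 also reacts only to a hazard ratio below 1.0, whereas the bias here lowers VE.

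**Working it through.** **1. The SAP's power.** Inputs from SAP 3: 500,000 people, 15% exposed (75,000 against 425,000), event probabilities 0.0036 and 0.0048, HR 0.80, two-sided alpha 0.05.

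- Events: 75,000 × 0.0036 + 425,000 × 0.0048 = 270 + 2,040 = 2,310.
- Allocation: k = 75,000/425,000 = 0.1765.
- Two-group survival formula: power = Φ(√(k × events) × |HR − 1| / (k × HR + 1) − 1.96) = Φ(20.19 × 0.20/1.141 − 1.96) = Φ(1.58) = 94.3%.

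The SAP states 94%, so the figure reproduces. (0.0036/0.0048 is 0.75, not 0.80, but the formula uses the probabilities only to count events.)

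**2. Dilution formula.** Let m and b be the shares of the reference cohort with missed Trumenba and missed Bexsero. With no missed Bexsero among the exposed:

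observed HR = HR_T / (1 − m − b + m × HR_T + b × HR_B)

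HR_B is 0.60 or 0.74, from the 40% and 26% in Protocol 7. The documents do not give m or b; the values below are assumptions. Power uses the formula in step 1 at the observed HR, with events held at 2,310.

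**3. Results at true HR_T 0.80 (VE 20%), missed doses in the reference cohort only.** Where two values are shown, the first is for HR_B 0.60 and the second for 0.74.

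| Missed share | Observed HR | VE | Power |
|---|---|---|---|
| Trumenba 5% | 0.80/0.99 = 0.808 | 19.2% | 92.4% |
| Trumenba 10% | 0.80/0.98 = 0.816 | 18.4% | 90.0% |
| Bexsero 5% | 0.80/0.98; 0.80/0.987 | 18.4%; 18.9% | 90.0%; 91.7% |
| Bexsero 10% | 0.80/0.96; 0.80/0.974 | 16.7%; 17.9% | 83.5%; 88.3% |
| Both 10% | 0.80/0.94; 0.80/0.954 | 14.9%; 16.1% | 74%; 81% |

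**4. Near the null.**

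- Missed Trumenba produces no bias at HR_T 1.0.
- Missed Bexsero of 10% in the reference cohort only, at HR_T 1.0: 1/0.96 and 1/0.974 give VE −4.2% and −2.7%.
- The same at the cited HR_T 0.97: 0.97/0.96 and 0.97/0.974 give VE −1.0% and +0.4%.

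**5. If exposed people also have missed Bexsero.** Assume that a person with both vaccines has the lower of the two hazards.

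- Equal shares of 5%, HR_B 0.74: (0.95 × 0.80 + 0.05 × 0.74)/0.987 = 0.8075, VE about 19.3%. With HR_B 0.60: 0.79/0.98 = 0.806, VE 19.4%.
- 10% of the exposed against 5% of the reference: VE 20.4% (HR_B 0.60) or 19.6% (HR_B 0.74).

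**The case against.** The strongest reply is that Protocol 9.9 already discloses the Trumenba part with the right direction, and that its likely size is modest: 5 to 10% missed costs one to two VE points. That is fair on size. What remains is that disclosure comes with no restriction, no sensitivity analysis and no report of pre-index enrolment, and that Bexsero is left out.

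The uneven division of missed Bexsero is an inference. No minimum gap between MenACWY and Trumenba is set, so exposed people can also have short histories; with equal shares most of the bias goes. This objection stands.

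Three stronger readings are tempting, and the documents do not support them:

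- *A null result could not be told apart from misclassification.* Missed Trumenba alone cannot take a real effect to zero, and power is still 90% at 10% missed.
- *Missed shares of 20% or more are plausible.* With 15% exposed, missing Trumenba in 20% of the other 85% gives 15 + 17 = 32%. That equals the entire 2021 coverage for any MenB vaccine in Protocol 7, leaving no room for Bexsero. Coverage among MenACWY recipients may differ, but the documents do not give it.
- *Missed first doses bias the two-dose analysis.* A person seen with one of two doses leaves the exposed group without entering the MenACWY-only group. On that account alone the cost is precision.

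A mandatory look-back also has a price. By the SAP's formula, halving the cohort gives Φ(3.54/√2 − 1.96) = Φ(0.54), about 71% power.

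**Conclusion.** The concern holds in a limited form. No pre-index enrolment is required, a missing claim counts as no vaccination, and the two cohorts face unequal observation requirements. For missed Trumenba in the one-dose analysis the bias toward zero follows from the cohort definitions. For missed Bexsero a downward bias is likely but not certain, and it can carry VE below zero when the true effect is small.

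The loss is one to two VE points for 5 to 10% missed Trumenba, and about four to five points with power of 74 to 81% if 10% of each vaccine is missed in the reference cohort. These sizes rest on assumed shares, on a true VE of 20%, and, for Bexsero in the table, on none being missed among the exposed. They justify measuring the problem; they do not justify replacing the main cohort.

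**What to change.** Keep the main cohort and make these changes:

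- **SAP 7.2.1.2:** add a sensitivity analysis of the primary VE restricted, in both cohorts alike, to people with a stated minimum of continuous enrolment before zero time. 365 days is an example, not a figure from the documents; a longer look-back can be added. State zero time for the reference cohort first: Protocol 9.1 uses the last MenACWY dose and SAP 2.1 the first.
- **Protocol 9.2.2 and SAP 4.1:** apply the Bexsero exclusion and the prior-Trumenba check to all observed claims history. Reconcile these sections with Protocol 9.2 on Bexsero given before the study, and say which claims would be searched.
- **SAP Tables 1.1 and 1.2:** report the length of pre-index enrolment by cohort.
- **Protocol 9.9:** add missed Bexsero, with its direction and the condition on which it depends.

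The cost is one filter on enrolment data that the source already holds (Protocol 9.4) and a few table rows. The restricted analysis will have a wider confidence interval and will select longer-insured people, so a change in VE could not be put down to misclassification alone. If only claims from 2016 onward are used, a 365-day rule also removes almost everyone with zero time in 2016. No look-back recovers doses never billed to the plan.

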9.2.2. Exclusion Criteria

Patients meeting any of the following criteria will not be included in the study:

Individuals having any dose of Bexsero at any time during 01 January 2016 and 31 December 2021 and prior to the study

Individuals with missing demographic variables or dates of outcome diagnoses or vaccine administration (listed in Section 9.3).

9.3. Variables

In this study, the variables of interest are age, gender, state of residence, date of vaccination and the date of disease diagnosis.

PFIZER CONFIDENTIAL CT24-WI-GL02-RF02 4.0 Non-Interventional Study Protocol Template For Secondary Data Collection Study 01-Jun-2022 Page 12 of 22

Table 1.Variable List

Variable	Role	Operational Definition
Birth Year	Covariate	Birth year (age to be calculated based on July 1 of birth year)
Gender	Covariate	Male, Female, Unknown
Residence (ZIP code)	Covariate	First 3 digits of the zip code from individuals' most recent enrollment
MenACWY vaccination	Non-exposure	Current procedural terminology (CPT) codes and National Drug Codes (NDC) listed below
Trumemba vaccination	Exposure	CPT and NDCs listed below
Gonococcal infection	Primary Outcome	ICD-10-CM codes listed below
Chlamydial infection	Reference disease Outcome	ICD-10-CM codes listed below

Code	Туре
A540	ICD-10-CM
A5400	ICD-10-CM
A5401	ICD-10-CM
A5402	ICD-10-CM
A5403	ICD-10-CM
A5409	ICD-10-CM
A541	ICD-10-CM
A542	ICD-10-CM
A5421	ICD-10-CM
A5422	ICD-10-CM
A5423	ICD-10-CM
A5424	ICD-10-CM
A5429	ICD-10-CM
A543	ICD-10-CM
A5430	ICD-10-CM
A5431	ICD-10-CM
A5432	ICD-10-CM
A5433	ICD-10-CM
A5439	ICD-10-CM
A544	ICD-10-CM
A5440	ICD-10-CM
A5441	ICD-10-CM
A5442	ICD-10-CM
A5443	ICD-10-CM
A5449	ICD-10-CM
A545	ICD-10-CM
A546	ICD-10-CM
A548	ICD-10-CM
A5481	ICD-10-CM
A5482	ICD-10-CM
A5483	ICD-10-CM
A5484	ICD-10-CM
A5485	ICD-10-CM
A5486	ICD-10-CM
A5489	ICD-10-CM
A549	ICD-10-CM

Table 2. Diagnosis Codes for Identifying Gonococcal Infections

Code	Туре
A55	ICD-10-CM
A560	ICD-10-CM
A5600	ICD-10-CM
A5601	ICD-10-CM
A5602	ICD-10-CM
A5609	ICD-10-CM
A561	ICD-10-CM
A5611	ICD-10-CM
A5619	ICD-10-CM
A562	ICD-10-CM
A563	ICD-10-CM
A564	ICD-10-CM
A568	ICD-10-CM
A71	ICD-10-CM
A710	ICD-10-CM
A711	ICD-10-CM
A719	ICD-10-CM
A74	ICD-10-CM
A740	ICD-10-CM
A748	ICD-10-CM
A7481	ICD-10-CM
A7489	ICD-10-CM
A749	ICD-10-CM

 Table 3.
 Diagnosis Codes for Identifying Chlamydial Infections

Code	Туре	Description
90734	CPT	Menactra/Menveo Vaccination
90619	CPT	Menquadfi Vaccine
49281-0589-05	NDC	Menactra Vaccine
46028-0208-01	NDC	Menveo Vaccine
58160-0955-09	NDC	Menveo Vaccine
49281-0589-58	NDC	Menactra Vaccine
49281-0590-58	NDC	Menquadfi Vaccine
46028-0218-11	NDC	Menveo Vaccine
58160-0958-01	NDC	Menveo Vaccine
58160-0959-01	NDC	Menveo Vaccine
46028-0219-11	NDC	Menveo Vaccine
54569-5687-01	NDC	Menactra Vaccine
50090-1890-01	NDC	Menactra Vaccine
49281-0590-05	NDC	Menquadfi Vaccine

Table 4.Current Procedural Terminal Codes and National Drug Codes for
Identifying MenACWY Vaccination

Table 5.Current Procedural Terminal Codes and National Drug Codes for
Identifying Trumemba (fHbp) Vaccination

Code	Туре	Description
90621	CPT	Trumenba Vaccination
00005-0100-01	NDC	Trumenba Vaccine
00005-0100-02	NDC	Trumemba Vaccine
00005-0100-05	NDC	Trumenba Vaccine
00005-0100-10	NDC	Trumenba Vaccine

Code	Туре	Description
90620	CPT	Meningococcal recombinant
		protein and outer membrane
		vesicle (OMV) vaccine,
		serogroup B (MenB-4C), 2
		dose schedule, for
		intramuscular use
46028011401	NDC	Bexsero vaccine
46028011402	NDC	Bexsero vaccine
46028011411	NDC	Bexsero vaccine
58160097602	NDC	Bexsero vaccine
58160097606	NDC	Bexsero vaccine
58160097620	NDC	Bexsero vaccine

Table 6.Current Procedural Terminal Codes and National Drug Codes for
Identifying Bexsero 4CMenB Vaccination

Additional details will be include in the Statistical Analysis Plan (SAP).

9.4. Data Sources

The data for this retrospective secondary data analysis is a large third party payer database, the IQVIA PharMetrics Plus (Pfizer 03 April 2023 version). PharMetrics Plus is a health plan claims database comprised of fully adjudicated medical and pharmacy claims for more than 210 million unique enrollees since 2006. Data contributors to the database are largely commercial health plans. It is representative of the commercially insured US national population for patients under 65 years of age. It contains a longitudinal view of inpatient and outpatient services, prescription and office/outpatient administered drugs, costs, and detailed enrollment information. All data are compliant to the Health Insurance Portability and Accountability Act (HIPAA) to protect patient privacy. The database is used in a variety of life sciences and commercial effectiveness studies. Over 250 peer reviewed publications have used PharMetrics Plus data.

9.5. Study Size

This is an exploratory study, thus no hypothesis was generated. All eligible individuals will be included in the study.

For the sample size estimation, we wished to detect a vaccine effectiveness against gonococcal infection of 20% or more with an onset from 14 days after receipt of both TRUMENBA and MenACWY. A Cox regression of the log hazard ratio on a covariate with a standard deviation of 1.50 to achieve 80% power at a 0.05 significance level to detect a regression coefficient equal to -0.2200, we need a sample of 15,669. The sample size was adjusted for an anticipated overall event rate of 0.0046. We will have 520,392 samples in the study database illustrating that we have adequate samples to conduct the analysis.

PFIZER CONFIDENTIAL

CT24-WI-GL02-RF02 4.0 Non-Interventional Study Protocol Template For Secondary Data Collection Study 01-Jun-2022 Page 17 of 22

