9.7. Data Analysis

The zero time is the date of Trumenba vaccination for the exposed group and the date of MenACWY for the unexposed group. We will assess gonococcal infections that occurred between i) 14 days after zero time and 365 days ii) 14 days after zero time and 730 days, iii) 14 days after zero time and 1095 days, and iv) 14 days after zero time and till end of the study period (31Dec2022). We will censor the data in the event of interest, death date (if known), plan disenrollment (if known), target end date, or the end of the study period, whichever comes first. In descriptive analyses, we will fit Kaplan-Meier curves. We will also create unadjusted and covariate adjusted Cox proportional hazard regression models verifying first that the proportionality assumption was satisfied for all independent variables. Hazard ratios (HRs) will be estimated by exponentiation of the coefficient for the vaccine variable in these models, with vaccine effectiveness estimated as (1–HR)×100%. SEs for the coefficients will be used to estimate p values and CIs for the HRs. If a covariate does not satisfy the assumption of proportionality, we will exclude the variable for the multivariable model and will perform the stratified analysis using the covariate.

Detailed methodology for summary and statistical analyses of data collected in this study will be documented in a statistical analysis plan (SAP), which will be dated, filed and maintained by Pfizer. The SAP may modify the plans outlined in the protocol; any major modifications of primary endpoint definitions or their analyses would be reflected in a protocol amendment.

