3 HYPOTHESES AND DECISION RULES

PFIZER CONFIDENTIAL CT24-WI-GL03-RF03 2.0 Non-Interventional Statistical Analysis Plan For Secondary Data Collection Study 01-Jun-2020 Page 6 of 28 This is an exploratory study, thus no hypothesis will be tested. There will be more than 500,000 individuals in which approximately 15% will be the experimental group. Assming a total of 500,000 subjects, and the probability of failure in the experimental group over the maximum time period of the study is 0.0036 and the probability of failure in the control group over the maximum time period of the study is 0.0048. This provides a power of 94% assuming a hazard ratio of 80% (20% vaccine effectiveness) and at an alpha of 0.05. The calculation was made using "powerSurvEPI" package under RStudio (Version 1.1.453).

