7.2.1.1 Primary Endpoint - Main Analysis

Vaccination Status

If a participant received at least one dose of Trumenba and at least one dose of MenACWY vaccine will be considered as vaccinated (exposed population).

Analysis

We will assess gonococcal infection that occurred between 14 days after zero time and till end of the study period. We will censor the data at death date (if known), plan disenrollment, or the end of the study period, whichever comes first. In descriptive analyses, we will fit Kaplan-Meier curves. We will also create unadjusted and covariate adjusted Cox proportional hazard regression models with time varying approach verifying first that the proportionality assumption was satisfied for all independent variables. Since the individuals entered into the surveillance at different points of time, we will employ the computing process algorithm of the proportional hazard model where the date of entry and the date of end of follow-up will be used in the model instead of time contribution to compute the hazard ratios.

Hazard ratios (HRs) will be estimated by exponentiation of the coefficient for the vaccine variable in these models, with vaccine effectiveness estimated as $(1-HR)\times100\%$. Standard errors (SEs) for the coefficients will be used to estimate p-values and 95% CIs for the HRs. If a covariate does not satisfy the assumption of proportionality, we will exclude the variable for the multivariable model and will perform the stratified analysis using the covariate. Both crude and adjusted VE with its corresponding 95% CI will be calculated.

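### Protocol 9.5 reaches N = 15,669 by giving a yes/no vaccine exposure a standard deviation of 1.50; the most it can be is 0.50, so the stated N is at least 9 times too small

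*Protocol*

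**What the plan says.** Protocol 9.5 (Study Size) aims to detect a vaccine effectiveness of 20% or more against gonococcal infection. It describes a Cox regression on "a covariate with a standard deviation of 1.50 to achieve 80% power at a 0.05 significance level", and continues "to detect a regression coefficient equal to -0.2200, we need a sample of 15,669", with an overall event rate of 0.0046. It concludes: "We will have 520,392 samples in the study database illustrating that we have adequate samples to conduct the analysis".

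Protocol 9.7 says which coefficient carries the effectiveness estimate: "Hazard ratios (HRs) will be estimated by exponentiation of the coefficient for the vaccine variable in these models". SAP 7.2.1.1 makes that variable a two-category one: a participant who "received at least one dose of Trumenba and at least one dose of MenACWY vaccine will be considered as vaccinated" is exposed. The reference cohort (Protocol 9.1, SAP 2.1) had MenACWY and no Trumenba.

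SAP section 3 gives a separate calculation for two groups. It says "There will be more than 500,000 individuals in which approximately 15% will be the experimental group", takes failure probabilities of 0.0036 (exposed) and 0.0048 (control) with 500,000 subjects, and states "This provides a power of 94% assuming a hazard ratio of 80% (20% vaccine effectiveness) and at an alpha of 0.05".

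**The concern.** The coefficient of -0.22 is close to ln(0.80) = -0.2231, the log hazard ratio for 20% effectiveness. The covariate being sized is therefore the vaccine indicator. A 0/1 variable with exposed share p has standard deviation sqrt(p(1-p)), which peaks at 0.50 when p = 0.5. A value of 1.50 is impossible for it, and Protocol 9.5 gives no reason for choosing it. The required N is inversely proportional to the variance of the covariate, so an inflated standard deviation shrinks N by the square of the inflation.

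At stake is what a reader may conclude from the comparison in 9.5. Set against 15,669, a database of 520,392 looks so large that every planned analysis would seem secure, including the narrower ones (at least two doses, ages 16-23, the first 12 months). Anyone interpreting a null result there needs the real margin.

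**Working it through.** **Inputs.** Coefficient b = -0.22, covariate SD 1.50, event rate 0.0046, 80% power, alpha 0.05 and available N 520,392 come from Protocol 9.5. Two-sided testing comes from SAP 3.2, because 9.5 does not give sidedness. The exposed share of about 15% and the failure probabilities come from SAP section 3.

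**Formula.** For a Cox model with a general covariate (the Schoenfeld formula in its Hsieh-Lavori form, with no correlation between exposure and the other covariates):

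events D = (1.960 + 0.842)^2 / (SD^2 x b^2), and N = D / 0.0046. The numerator is 7.849.

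**Reproducing the protocol's figure.** D = 7.849 / (1.50^2 x 0.22^2) = 7.849 / 0.1089 = 72.07. N = 72.07 / 0.0046 = 15,668.3, which rounds up to the stated 15,669. A one-sided test would give 12,342, so the two-sided method and the inputs are identified.

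**Replacing only the SD.**

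| Exposed share | SD | b | Events | N | Multiple of 15,669 |
|---|---|---|---|---|---|
| 50% (best case) | 0.500 | -0.22 | 649 | 141,015 | 9.0 |
| 15% | 0.357 | -0.22 | 1,272 | 276,499 | 17.6 |
| 15% | 0.357 | ln(0.80) | 1,236 | 268,764 | 17.2 |

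The 9-fold floor is (1.50/0.50)^2 and does not depend on the exposed share. At 15% exposed the ratio of variances is 2.25/0.1275 = 17.6. The last row also changes b, so it mixes in a small second effect.

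**Power that 15,669 people would give.** Events = 15,669 x 0.0046 = 72.1. Power = Phi(sqrt(D) x SD x |b| - 1.96). At 15% exposed this is Phi(sqrt(72.1 x 0.1275) x 0.22 - 1.96) = Phi(-1.29), about 10%. At 50% exposed it is about 15%.

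**Power with the available 520,392.** Events = 520,392 x 0.0046 = 2,394. At 15% exposed, power is about 97%. By this formula it stays at 80% or more down to an exposed share of about 7.3%.

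**Checking the SAP calculation.** The 94% reproduces with a Freedman-type two-group formula, power = Phi(sqrt(k x m) x |HR - 1| / (k x HR + 1) - 1.96):
- k = 75,000/425,000 = 0.1765 and HR = 0.80.
- m = 75,000 x 0.0036 + 425,000 x 0.0048 = 2,310 events.
- Power = 94.3%.

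Solved for 80% power, the same formula needs 1,448 events, so N = 1,448 / 0.0046, about 314,800, or 20 times 15,669.

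**Margins.** 520,392/15,669 = 33.2. Against the corrected figures at 15% exposed: 520,392/268,764 = 1.94, 520,392/276,499 = 1.88 and 520,392/314,800 = 1.65.

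**Sensitivity for narrower analyses.** 1,272/2,394 = 53%. At 15% exposed, a follow-up window holding less than about 53% of the events falls below 80% power. The documents do not give event counts by window or subset, so this shows how thin the margin is and does not predict a shortfall.

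**The case against.** The strongest reply is that nothing operational depends on 15,669. The study is labelled exploratory, uses existing claims data and takes in everyone eligible. The figure fixes no enrolment, data cut or analysis. The SAP already has a sound two-group calculation, and the protocol's stated conclusion, that the sample is adequate, is correct. All of that stands, and it limits the consequence. It does not make the N and power printed in 9.5 correct.

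Nor does 9.5 state a 33-fold margin. It prints two numbers and calls the sample adequate; the ratio is my division. That is fair, although the comparison of those two numbers is the only support 9.5 offers.

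Could the covariate be something else, such as a dose count? If every exposed person had the same count, an SD of 1.50 at 15% exposed would need 1.50/0.357 = 4.2 doses each. In addition, -0.22 would then be a per-dose effect and not the 20% effectiveness of the at-least-one-dose contrast. This reading fails.

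The 15% share is approximate. The SAP's failure probabilities weighted at 15% give 0.15 x 0.0036 + 0.85 x 0.0048 = 0.00462, which agrees with the protocol's 0.0046. However, any share from about 12.5% to 20.8% rounds to the same rate, which puts N between about 322,000 and 214,000 with b = -0.22. Only the 9-fold floor is free of this assumption.

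**Conclusion.** The concern holds. The arithmetic in 9.5 is exact, but one input is impossible for the variable it describes. The stated 15,669 therefore does not give 80% power for 20% effectiveness. It is too small by at least 9 times, by 17.6 times at 15% exposed with the protocol's own coefficient, and by about 20 times with the formula type that reproduces the SAP's 94%.

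These figures take the event rate of 0.0046 as given and assume exposure is uncorrelated with age, sex and region. Any such correlation raises the N needed for the adjusted model, so they are minimums.

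The primary analysis remains adequately sized, and the finding calls for a correction to the justification, not to the design. The study-size calculations in the two documents also need to agree: the SAP's uses two groups, while the protocol's uses an SD that no two-group exposure can have.

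**What to change.** In Protocol 9.5, withdraw the SD of 1.50 and the 15,669, and state the SAP section 3 calculation instead: 500,000 individuals, about 15% exposed, hazard ratio 0.80, two-sided alpha 0.05, 94% power.

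When copying it across, correct one detail. The SAP's failure probabilities have a ratio of 0.0036/0.0048 = 0.75, not 0.80. Using 0.80 x 0.0048 = 0.00384 for the exposed group gives 2,328 events and 94.4% power, so the 94% is unaffected.

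If a required N is to be kept as well, compute it with SD = sqrt(0.15 x 0.85) = 0.357 and ln(0.80), which gives about 1,240 events and about 269,000 individuals. Name the formula (Schoenfeld type), because the Freedman type behind the SAP's 94% asks for about 315,000.

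The cost is one or two sentences in the protocol. Data, eligibility and analysis do not change; the margin on display becomes smaller.
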